6.2.1 Baseline and Change from Baseline	Maximum absolute change from baseline will be calculated as the maximum of the absolute changes from baseline over all visits during treatment period.	Maximum change from baseline will be calculated as the maximum of the changes from baseline over all visits during treatment period.
8.2.1 Change in FIX levels from pre-dose	Actual and change from baseline (including maximum absolute change from baseline) values for FIX activity level will be summarized by time point for the PK and the Safety Population. Different PK parameters will be summarized as well as described in Section Error! Reference source not found.	Actual and change from baseline (including maximum change from baseline) values for FIX activity level will be summarized by time point for the PK and the Safety Population. Different PK parameters will be summarized as well as described in Section Error! Reference source not found.
9.3.2 Listing and Presentation of Individual PK Data	The following figures will be produced: Individual intense PK concentration-time provided for FIX activity levels with all subjects in the same figure on linear scales.	The following figure will be produced: Box plots of PK concentration provided for FIX activity levels by visits.
9.3.3 Summary of PK Concentrations and Parameter in Plasma		Added: Geometric CV = sqrt (exp ((log (geometric SD)) ^2) - 1) * 100%
9.4 PK Parameters Derivation: Attainment of Steady State for FIX Activity		Added: REPEATED <time> /type = un SUBJECT = <subject>
10.2 PD Biomarkers Analysis	Actual and change from baseline (including maximum absolute change from baseline) for all PD parameters (e.g., Prothrombin Time, aPTT, Fibrinogen, D-dimer, F1+2, and TAT) will be summarized by time point. Coagulation assays and thrombogenicity markers will be tabulated separately.	Actual and change from baseline (including maximum change from baseline) for all PD parameters (e.g., Prothrombin Time, aPTT, Fibrinogen, D-dimer, F1+2, and TAT) will be summarized by time point. Coagulation assays and thrombogenicity markers will be tabulated separately. Added: In case that thrombogenicity markers are below limit of quantification, then all analysis are done with the imputed midpoint of the potential values

This document is confidential.

Note to File, 24-July-2020
Sponsor: Catalyst Biosciences; Protocol No.: DLZ-201

Section	Revised from	Revised to
		for this observation. For coagulation assays, the limit of quantification is used for the analysis.
10.3 Presentation of PD Data	Removed: Individual PD data-time profiles of thrombogenicity markers for actual measurement and change from baseline results will be presented with all subjects in the same figure on linear scales. Mean +/- SD PD data-time profiles of thrombogenicity markers for actual measurements and change from baseline results will be presented in the same figure.	Box plots of thrombogenicity markers for actual measurements will be presented by visit.
11.4 Laboratory Evaluations	Descriptive statistics will be calculated for each numeric laboratory test parameter by visit for actual values and change from baseline (including maximum absolute change from baseline).	Descriptive statistics will be calculated for each numeric laboratory test parameter by visit for actual values and change from baseline (including maximum change from baseline).
11.5 Vital Signs	Descriptive summaries of actual values and changes from study baseline will be calculated for vital signs by visit, which includes BP, HR, RR, body temperature (in C), weight and BMI. In addition, change from baseline (including maximum absolute change from baseline) will be summarized.	Descriptive summaries of actual values and changes from study baseline will be calculated for vital signs by visit, which includes BP, HR, RR, body temperature (in C), weight and BMI. In addition, change from baseline (including maximum change from baseline) will be summarized.
title of output 14.3.1.6	Treatment Emergent Serious Adverse Events by Relationship to Study Drug by System Organ Class and Preferred Term (Safety Population)	Treatment Emergent Serious Adverse Events by Highest Relationship to Study Drug by System Organ Class and Preferred Term (Safety Population)
Title of output 14.2.2.1.3	Individual Profiles of FIX Activity Levels - Linear Scale (PK Population)	Box Plots of FIX Activity Levels (PK Population)
Title of output 14.2.2.3.3	Removed: Individual PD Profiles - Linear Scale (PD Population)	
Title of output 14.2.2.3.3	Mean (SD) PD Profiles of Thrombogenicity Markers (PD Population)	Box Plots of Thrombogenicity Markers (PD Population)
Title of output 16.2.4.2.3	Hemophilia Bleed History (Safety Population)	Hemophilia Bleed History in the last 6 Months (Safety Population)

Bolded=added/revised; Strikethrough=removed.

This document is confidential.

Note to File, 24-July-2020

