9.4. PK Parameters Derivation: Attainment of Steady State for FIX Activity

Attainment of steady state will be estimated using aggregate assessment of trough concentration if sufficient data will be available.

To assess whether steady state was achieved for FIX activity after daily dosing of CB2679d, aggregate assessment of trough concentration will be used to evaluate attainment of steady state (Maganti et al 2008). The approach is based on the comparison of log-transformed normalized trough concentration values for each dose to the mean of the results for all the following doses.

This analysis will be done using repeated measures analysis only if the data are sufficient to support; i.e., analysis will be carried out only on subjects who have at least 3 valid FIX activity level results out of 6 pre-dose samples). Alternatively, analysis of variance (ANOVA) comparison will be carried out on log-transformed Cmin (concentration at the end of the dosing interval = FIX activity level pre-dosing) pre-dose on days 2, 3, 7, 14, 21 and 28. The following SAS code may be used to conduct the analysis:

PROC MIXED;

CLASS <time> <subject>;

MODEL log_base_e_ <FIX actual level> = <time> /DDFM = KR;

LSMEANS <time>;

RUN;

The DDFM = KR (Kenward Roger) option performs the degrees-of-freedom calculations detailed by Kenward and Roger (1997).

Contrasts will be tested between a time point and the pooled mean over all remaining time points. For example, the following contrasts will be tested as example:

- Day 3 vs Days 7, 14, 21, and 28
- Day 7 vs Days 14, 21, and 28
- Etc.

The first non-significant comparison will be concluded to be the dosing interval at which steady state concentration are attained. The p-value for difference of Least Square Means (LSM), Geometric Mean Ratio, and the 95% confidence interval (CI) for the contrasts will be provided.

This document is confidential.

Statistical Analysis Plan for Interventional Studies
Sponsor: Catalyst Biosciences, Inc.; Protocol No.: DLZ-201

10. Analysis of Pharmacodynamics

PD analysis will be performed using SAS statistical package version 9.4 or higher. PD analysis will be performed for PD and Safety Population.

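### The unstructured covariance added for the steady-state analysis cannot be estimated with six subjects and six troughs, and the first non-significant contrast is then read as proof of steady state

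*SAP*

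**What the plan says.** SAP 9.4 analyses log FIX activity at the "FIX activity level pre-dosing) pre-dose on days 2, 3, 7, 14, 21 and 28". The code fits one mean per day, "MODEL log_base_e_ <FIX actual level> = <time> /DDFM = KR", and the Note to File adds "REPEATED <time> /type = un SUBJECT = <subject>". Each day is contrasted with the pooled mean of the later days. The example list opens with "Day 3 vs Days 7, 14, 21, and 28", so it is not clear whether Day 2 stays in the model. A p-value, geometric mean ratio and 95% CI are promised for each contrast. The conclusion is then drawn by rule: "The first non-significant comparison will be concluded to be the dosing interval at which steady state concentration are attained".

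Two provisions qualify this. First, "This analysis will be done using repeated measures analysis only if the data are sufficient to support", which is spelled out as an analysis of "subjects who have at least 3 valid FIX activity level results out of 6 pre-dose samples". Second, "Alternatively, analysis of variance (ANOVA) comparison will be carried out on log-transformed Cmin"; what triggers the alternative is not stated.

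SAP 3.5 plans 6 subjects without a formal calculation, and SAP 6.3 does not impute missing data. No significance level, ratio margin or minimum number of subjects is given for these contrasts.

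**The concern.** There are two independent faults.

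(a) An unstructured matrix for six days has 6 × 7 / 2 = 21 parameters. Six subjects, less one degree of freedom for each day's mean, leave five independent residual vectors. Five vectors cannot determine a 6 × 6 covariance matrix.

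(b) The rule treats failure to detect a difference as evidence that none exists. The less information the trial yields, the earlier steady state is declared.

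The primary objective (SAP 3.1) concerns a steady-state level, and SAP 9.4 is the only stated test of that qualifier. The outputs at risk are Tables 14.2.3.1 and 14.2.3.2 and any steady-state statement drawn from them. As the text stands, another model would have to be chosen after the fit had failed.

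**Working it through.** The plan gives no power or precision figure for this analysis, so there is nothing of its own to reproduce.

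**Estimability.** For complete data, with a free mean per day, the REML log-likelihood is, up to a constant,

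−½[(n − 1) ln|Σ| + tr(Σ⁻¹S)],

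where S is the residual sums-of-squares matrix. If S has a null direction, let the variance ε in that direction go to 0. The trace stays bounded and the log-likelihood grows as ((n − 1)/2) ln(1/ε). For n = 6, each hundredfold fall in ε adds 2.5 × ln 100 = 11.5.

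Simulated data, ε = 1e-2, 1e-4, 1e-6, 1e-8:

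| Subjects × days | Residual rank | REML log-likelihood | Finite solution? |
|---|---|---|---|
| 6 × 6 complete | 5 of 6 | 37.1, 48.7, 60.2, 71.7 | No |
| 6 × 5 (no Day 2), complete | 5 of 5 | bounded | Yes, median condition number about 420 (true value 6) |
| 6 × 5, one subject lacks Day 28 | – | 30.9, 40.2, 49.4, 58.6 | No |
| 6 × 5, one subject lacks a middle day | – | 25.4, 34.6, 43.8, 53.0 | No |
| 7 × 6 complete | 6 of 6 | bounded | Yes, median condition number about 700 (true value 7) |

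With one trough missing from 6 × 5, the step is (4/2) × ln 100 = 9.2, as seen. Condition numbers assume a compound-symmetric truth with correlation 0.5. Seven subjects with one missing trough also diverge. A replacement under SAP 5.1 therefore does not rescue the six-day model if the replaced subject has no Day 28 trough.

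The point estimates survive. With complete data the least-squares means agree under identity and unstructured covariance (largest difference 3e-16), so the geometric mean ratios are unaffected. Where type=un does fit (6 × 5 complete), its contrast variance equals that of the per-subject contrast (0.023756 for both).

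**The decision rule.** Inputs: half-life 63.2 h (Protocol 2.2.2); subcutaneous accumulation only, IV load ignored; five troughs from Day 3; two-sided 0.05, assumed from the 95% CI; log SD = √ln(1 + CV²), with within-subject CV assumed because the documents do not give it.

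Fraction of plateau before dosing on day d = 1 − 2^(−24(d − 1)/63.2). This gives 0.409, 0.794, 0.967, 0.995 and 0.999 for Days 3, 7, 14, 21 and 28.

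Percentage of trials naming Day 7 (79% of plateau) as steady state, n = 6:

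| Within-subject CV | 10% | 15% | 25% | 35% |
|---|---|---|---|---|
| Per-subject contrasts | 5 | 30 | 67 | 79 |
| Compound symmetry | 1 | 16 | 57 | 74 |

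Percentage declaring by Day 7, per-subject contrasts:

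| n | 4 | 6 | 12 | 24 |
|---|---|---|---|---|
| CV 15% | 58 | 30 | 2 | 0 |
| CV 25% | 81 | 67 | 32 | 5 |

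The only documented spread is cohort 5 in Protocol 2.2.2 (n = 5, median 15.7%, quartiles 14.9% and 16.6%, one subject not above 12%). The narrowest consistent values are 12, 14.9, 15.7, 16.6 and 16.6, with log SD 0.135, a CV of 13.5%. This is a lower bound on total CV at one time point. It does not fix the within-subject part.

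**The ANOVA alternative.** Its model is not written out. In the revised code subject enters through REPEATED, so its absence from MODEL matters only here. Without a subject term, at within-subject CV 10%, Day 7 is named in 4.5% of trials against 4.4% with per-subject contrasts if between-subject CV is 9% (√(0.135² − 0.10²) = 0.09). If between-subject CV is 30% (assumed), the figures are 76% against 5%.

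**The case against.** The strongest reply is that the plan has an exit: repeated measures only when data suffice, ANOVA otherwise, and code that is only suggested. But sufficiency is defined by troughs per subject. Six complete subjects meet the condition and still cannot be fitted, so the text does not send the analyst to the ANOVA.

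It can also be said that a standard error still exists. That is right: with complete data each contrast has a valid paired standard error on 5 df, and the fault lies in the coded route to it. No SAS run was made, so what PROC MIXED would print is not claimed here.

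The percentages do not describe this design, because every subject receives a 50 IU/kg IV load. Adding it, with bioavailability 18.2–23.6%, puts Day 7 at 92–96% of plateau if the load decays at 63.2 h, and at about 80% if it decays at 20 h (assumed). The Day 7 error could then be small, although the load also raises the earliest troughs and may make Day 3 easier to name. The direction of the flaw remains; its size is unknown.

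Finally, the sequential contrast follows a cited published method, the study is descriptive, and ratios and intervals are printed beside the conclusion. This limits the harm but does not justify concluding steady state from non-significance.

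**Conclusion.** Both parts hold. Part (a) is algebra: at six subjects by six troughs the revised model has no finite REML solution, whatever the data. At six by five it needs all 30 troughs. Part (b) is a flaw in the stated rule and does not depend on the covariance. Its size rests on an undocumented within-subject CV and on ignoring the IV load: about 1–5% misnaming of Day 7 at CV 10%, rising to 74–79% at CV 35%. The effect is confined to Tables 14.2.3.1–2 and statements based on them. The ratios survive with complete data, and the SAP 8.1 count does not use this result. It should be fixed, but it does not undermine the primary count.

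**What to change.** Replace type=un with one named model that six subjects can support:

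- per-subject log contrasts (log trough on day k minus the mean log of that subject's available later troughs), with t-intervals on n − 1 df and the number of subjects shown for each contrast; or
- compound symmetry (random subject intercept) with Kenward-Roger df.

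State which days are in the model, require a subject term in any ANOVA fallback, and define sufficient data by number of subjects as well as troughs per subject.

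Delete the first-non-significant conclusion. Describe attainment from the planned ratios and 95% CIs, and say that a wide interval is inconclusive. If a yes/no statement is wanted, the sponsor should name the ratio margin in advance. Optionally, name Days 21 and 28 as reference troughs: at the longest earlier-study half-life, 103 h, 1 − 2^(−480/103) = 96.0% and 1 − 2^(−648/103) = 98.7% of plateau. Label this an assumption, not a result.

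The cost is SAP wording and a few lines of code. The downside is width. For Day 14 against the mean of Days 21 and 28 with a true ratio of 1, the log half-width is t × σ × √(1.5/6):

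| CV | 10% | 15% | 25% | 35% |
|---|---|---|---|---|
| Per subject, 5 df | 0.88–1.14 | 0.83–1.21 | 0.73–1.37 | 0.65–1.55 |
| Compound symmetry, five troughs, 20 df | 0.90–1.11 | 0.86–1.17 | 0.77–1.29 | 0.70–1.43 |

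Compound symmetry is tighter but assumes equal variances and correlations. The steady-state statement may come out less favourable than under the present rule.
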